10. PROTECTION OF HUMAN PARTICIPANTS

10.1. Patient Information

All parties will comply with all applicable laws, including laws regarding the implementation of organizational and technical measures to ensure protection of patient personal data. Such measures will include omitting patient names or other directly identifiable data in any reports, publications, or other disclosures, except where required by applicable laws.

The personal data will be stored at the study site in encrypted electronic and/or paper form and will be password protected or secured in a locked room to ensure that only authorized study staff have access. The study site will implement appropriate technical and organizational measures to ensure that the personal data can be recovered in the event of disaster. In the event of a potential personal data breach, the study site shall be responsible for determining whether a personal data breach has in fact occurred and, if so, providing breach notifications as required by law.

To protect the rights and freedoms of natural persons with regard to the processing of personal data, when study data are compiled for transfer to Pfizer and other authorized parties, patient names will be removed and will be replaced by a single, specific, numerical code, based on a numbering system defined by Pfizer. All other identifiable data transferred to Pfizer or other authorized parties will be identified by this single, patient-specific code. The investigator site will maintain a confidential list of patients who participated in the study, linking each patient's numerical code to his or her actual identity. In case of data transfer, Pfizer will maintain high standards of confidentiality and protection of patients' personal data consistent with the clinical study agreement and applicable privacy laws.

10.2. Patient Consent

The informed consent documents and any patient recruitment materials must be in compliance with local regulatory requirements and legal requirements, including applicable privacy laws.

The informed consent documents used during the informed consent process and any patient recruitment materials must be reviewed and approved by Pfizer, approved by the institutional review board (IRB)/ ethics committee (EC) before use, and available for inspection.

The investigator must ensure that each study patient, or his or her legally acceptable representative is fully informed about the nature and objectives of the study, the sharing of data

relating to the study, and possible risks associated with participation, including the risks associated with the processing of the patient's personal data. The investigator further must ensure that each study patient or his or her legally acceptable representative is fully informed about his or her right to access and correct his or her personal data and to withdraw consent for the processing of his or her personal data.

Whenever consent is obtained from a patient's legally acceptable representative, the patient's assent (affirmative agreement) must subsequently be obtained when the patient has the capacity to provide assent, as determined by the IRB/EC. If the investigator determines that a patient's decisional capacity is so limited that he or she cannot reasonably be consulted, then, as permitted by the IRB/EC and consistent with local regulatory and legal requirements, the patient's assent may be waived with source documentation of the reason assent was not obtained. If the study patient does not provide his or her own consent, the source documents must record why the patient did not provide consent (eg, minor, decisionally impaired adult), how the investigator determined that the person signing the consent was the patient's legally acceptable representative, the consent signer's relationship to the study patient (eg, parent, spouse), and that the patient's assent was obtained or waived. If assent is obtained verbally, it must be documented in the source documents.

The investigator, or a person designated by the investigator, will obtain written informed consent from each patient or the patient's legally acceptable representative, before any study-specific activity is performed unless a waiver of informed consent has been granted by an IRB/EC. The investigator will retain the original of each patient's signed consent document.

10.3. Patient Withdrawal

Patients may withdraw from the study at any time at their own request, or they may be withdrawn at any time at the discretion of the investigator or sponsor for safety, behavioral, or administrative reasons. In any circumstance, every effort should be made to document patient outcome, if applicable. The investigator would inquire about the reason for withdrawal and follow-up with the patient regarding any unresolved adverse events.

If the patient withdraws from the study, and also withdraws consent for disclosure of future information, no further evaluations should be performed, and no additional data should be collected. The sponsor may retain and continue to use any data collected before such withdrawal of consent.

Withdrawal criteria: Patients will receive the study treatment while it is considered to be in their best interest. Specifically, individual treatment of a given patient will continue until:

- Documented disease progression.
- Unacceptable toxicity after allowed dose reductions.
- Intercurrent illness of sufficient magnitude to preclude safe continuation of the study treatment.
- Patient's refusal (follow-up has to be continued for those patients who refuse treatment, but do not withdraw consent) and/or non-compliance with study requirements.
- A major protocol deviation that may affect the risk/benefit ratio for the participating patient.

- Requirement of > 2 dose reductions.
- Investigator's decision.

Patients who are withdrawn for any reasons must not be re-treated in the context of this study at any time. However, if the only reason for discontinuation is disease progression, the patient can be treated beyond radiological progression provided the patient is obtaining benefit from the treatment with good tolerance to the treatment, and the patient and sponsor agrees with the decision.

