9. RESEARCH METHODS

9.1. Study Design

This is an observational, non-interventional, prospective, multicenter and nationwide study with the category of PASS (Post Authorization Safety Study), which seeks to answer the research question: what is the spectrum of adverse events and mitigation strategies associated with lorlatinib in a real-world Spanish population? For this purpose, an observational, non-interventional and prospective study design is ideal to faithfully reflect what occurs in the routine clinical practice.

It is important to note that our study population exhibits a low incidence of NSCLC patients, approximately 3-4%. Consequently, the current study is descriptive in nature, as it lacks the statistical robustness (relatively small sample, but almost similar to the total of patients included in the pivotal trial) necessary to establish a significant association between a specific adverse event and the drug.

The primary objective will be to describe all the spectrum of the AEs of Iorlatinib (CTCAE v6.0) and its mitigation strategies with special interest in CNS AEs.

Primary Objective	Corresponding Endpoint			
To describe all the spectrum of the adverse events (AEs) of Lorlatinib (CTCAE v6.0) and its mitigation strategies, with special interest in CNS AEs	Occurrence (number of adverse events) and severity of AEs, with severity determined according to NCI CTCAE v6.0 criteria. Frequency and period of dose reductions as well as concurrent medications used to control AEs will be collected			
Secondary Objectives	Corresponding Endpoints			
To identify factors that are predictive of AEs, with special interest in CNS AEs	To evaluate the relationship of multiple demographic and clinical factors with the incidence of AEs, with special interest in CNS adverse events			
To evaluate the effectiveness of 1L lorlatinib in real-world practice	• Effectiveness will be assessed:			
rwPFS rate at 12 and 18 months in the ITT population with and without brain metastasis at baseline	1. To determine real-world progression-free survival (rwPFS) defined as the time from enrollment to the first occurrence of disease progression (intracranial or systemic) or death from any cause, whichever occurs first, as determined by the investigator using RECIST v1.1. criteria, at 12 and 18 months, in the ITT population with and without brain metastasis at baseline			

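### Three rules in section 10.3 let the sponsor or the study decide when lorlatinib stops, which contradicts the non-interventional design

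*Protocol*

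**What the plan says.** Section 10.3 opens with two paragraphs on leaving the study and on withdrawing consent. They are ordinary and not in dispute. The section then turns to the drug itself, under a label that still speaks of withdrawal: "Patients will receive the study treatment while it is considered to be in their best interest". It continues "Specifically, individual treatment of a given patient will continue until", followed by a list.

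The list holds progression, unacceptable toxicity, intercurrent illness, patient refusal, the investigator's decision, and three further items: "non-compliance with study requirements", "A major protocol deviation that may affect the risk/benefit ratio for the participating patient" and "Requirement of > 2 dose reductions".

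The closing paragraph says that withdrawn patients "must not be re-treated in the context of this study at any time". It then makes an exception for patients whose only reason to stop is progression. They may be treated beyond radiological progression if they benefit, tolerate the drug well, and "the patient and sponsor agrees with the decision".

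Section 9.1 calls the study observational and non-interventional and says that this "study design is ideal to faithfully reflect what occurs in the routine clinical practice".

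**The concern.** In a non-interventional study the treating physician decides on treatment and the study records what happens. Section 10.3 says instead, in the protocol's own voice, when treatment goes on and when it ends. It gives the sponsor a say in whether a patient stays on a prescribed drug after progression. It also makes a lapse in study requirements, or a departure from the protocol, a reason to end cancer treatment.

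What is at stake is the meaning of some of the results. The study sets out to describe how lorlatinib is used and managed in ordinary Spanish practice. Where a stop comes from one of these rules, the recorded treatment time describes the protocol and not the practice. Patient care is also at stake, because the text as written would guide it.

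**Working it through.** No formula applies, and the plan gives no figure to reproduce. The check sets the sections side by side.

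1. **Does the list govern the drug or study participation?** Its lead-in ("Specifically, individual treatment of a given patient will continue until") has treatment as its subject. The refusal item also requires follow-up to continue for patients who refuse treatment without withdrawing consent, so the list itself separates stopping the drug from leaving the study. It governs the drug.

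2. **What does the rest of the protocol say?**
   - Section 9.1: a non-interventional design chosen to mirror ordinary practice.
   - Section 9.2.1: lorlatinib was started 7 to 28 days before enrolment, in routine care.
   - Section 9.8: investigators work as they would in routine practice.
   - Section 9.9: the study only collects data and creates no risk or benefit for the patient.
   - Section 10.5: the study is run under the royal decree on non-interventional studies.

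3. **Which items conflict with that?**
   - *Sponsor agreement beyond progression:* conflicts. A sponsor that only collects data has no role in this decision.
   - *Stop for non-compliance with study requirements:* conflicts. It ties treatment to study conduct.
   - *Stop for a major protocol deviation:* conflicts for the same reason.
   - *Progression, toxicity, intercurrent illness, refusal, investigator's decision:* ordinary clinical reasons, no conflict.
   - *More than two dose reductions:* not shown to conflict. Sections 9.2 and 11.1 tie prescribing to the label, and the documents do not show what the label says on this.
   - *Re-treatment sentence:* limited to the context of the study. Its meaning is unclear where the study supplies no drug, but it is not a contradiction.

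4. **Does any other section override the three?** None limits them to participation or defers them to the treating physician. Sections 9.8 and 9.10.1 require compliance with the protocol, so the text is binding.

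5. **Which measurements could change?**
   - *Duration of treatment* (9.1) runs from first to last dose for any cause. A rule-driven stop shortens it whenever the physician would have continued.
   - *Time to next treatment* (9.1) starts at the end of lorlatinib, so its start point moves with that stop.
   - *Treatment after progression* (9.3) is recorded as yes or no, with the date of definitive discontinuation. A sponsor refusal would change it directly.

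6. **How many patients?** The protocol gives no rate of sponsor refusal, study non-compliance or major deviation, so no count or range can be derived. The sample size of 116 (9.5) rests on CNS adverse event incidences of 42% and 55% and 80% power. None of these inputs involves a treatment stop.

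**The case against.** The strongest defence is that this is leftover trial wording with little practical effect. Similar remnants appear elsewhere: section 11 mentions changes in study dosing and an investigational product, and it carries a footnote on an adjudication committee that the same section calls not applicable. The protocol prescribes so little beyond routine care that a deviation able to alter risk and benefit is hard to picture. Treatment beyond progression is permitted, so that variable can still be recorded. Section 9.2 also collects stop dates and reasons for discontinuation at each visit.

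Much of this stands. The effect is conditional on the rules being followed and may be small. It would also be wrong to infer that rule-driven stops could not be told apart, since the reason is collected. But a recorded reason only identifies the patient. It does not show how long treatment would have lasted in routine care. And leftover wording in a binding protocol is still binding.

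A reader might also infer three stronger points that the documents do not support:

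- **That the primary endpoint is distorted.** The primary endpoint includes dose reductions, but the only route to it is the limit of more than two, and whether that limit departs from the label cannot be seen here.
- **That about a third of patients are affected.** Section 7 reports that 49 of 149 lorlatinib patients in CROWN had a dose reduction, and 49/149 × 116 = 38.1. That figure counts patients with at least one reduction, over a median of 57.0 months of treatment. It says almost nothing about how many need more than two, and nothing about the three rules that do conflict.
- **That the re-treatment sentence bars prescribing.** It is confined to the study context, and section 9.9 confines the study to data collection.

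**Conclusion.** The point holds for three rules: sponsor agreement for treatment beyond progression, and treatment stops for study non-compliance and for a major protocol deviation. Each contradicts the stated non-interventional, routine-practice, data-collection-only design, and nothing else in the protocol corrects it.

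If followed, they could alter duration of treatment, the start point of time to next treatment, and treatment after progression. The size is unknown and cannot be bounded from the documents. The sample size is unaffected, and no effect on the primary endpoint is shown. The conclusion rests on reading the list as written, as rules about treatment, and on investigators following it. It should be corrected because it touches patient care and the declared nature of the study, and because the correction is cheap.

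**What to change.** Amend section 10.3 as follows:

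- Delete the sponsor-agreement condition for treatment beyond progression.
- Delete non-compliance and major protocol deviation as treatment stops, or recast them as reasons for leaving data collection.
- State that dosing, stopping, restarting and treatment beyond progression are decided by the treating physician under routine practice and the label, and are recorded as they occur.
- State that the end of lorlatinib is not withdrawal from the study, and that follow-up continues unless consent is withdrawn.
- Replace the limit on dose reductions with a reference to the label, or delete it if it goes beyond the label.
- Remove or clarify the re-treatment sentence, as a drafting point only.

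The cost is a short protocol amendment with ethics committee approval (9.10.1 and 10.4). No visits or data items are added: the section 9.2 schedule already collects stop dates, reasons, post-progression treatment and the date of death or last contact.

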10.4. Institutional Review Board (IRB)/ Ethics Committee (EC)

It is the responsibility of the investigator to have prospective approval of the study protocol, protocol amendments, and informed consent forms, and other relevant documents, (eg, recruitment advertisements), if applicable, from the IRB/EC. All correspondence with the IRB/EC should be retained by the investigator. Copies of IRB/EC approvals should be forwarded to Pfizer.

10.5. Ethical Conduct of the Study

The study will be conducted in accordance with legal and regulatory requirements, Royal Decree (RD) 957/2020 of 3 November 2020 regulating non-interventional studies on medicinal products for human use (RD 957/2020), including Royal Decree 577/2013 for safety, and Guideline on Good Pharmacovigilance Practices (GVP) - Module VI - Collection, management and submission of reports of suspected adverse reactions to medicinal products, General Data Protection Regulation (GDPR), Organic Law 3/2018, of December 5, on the Protection of Personal Data and the Guarantee of Digital Rights, as well as with scientific purpose, value, and rigor and follow generally accepted research practices described in Guidelines for Good Pharmacoepidemiology Practices (GPP)¹⁴.

11. MANAGEMENT AND REPORTING OF ADVERSE EVENTS/ADVERSE REACTIONS

Requirements

Table 6 summarizes the requirements for recording safety events on the CRF and for reporting safety events to the Pfizer Drug Safety Unit (DSU) on the Non-Interventional Study Adverse Event Report Form for Protocols with Stipulated Active Collection of Adverse Events herein after referred to as the NIS AEM Report Form.

These requirements are delineated for 5 types of safety events: (1) serious AEs (SAEs); (2) non-serious AEs (as applicable); and scenarios involving: (3) exposure during breast feeding, medication error, overdose, misuse, extravasation, lack of efficacy; (4) exposure during pregnancy (EDP), and (5) occupational/environmental exposure. These events are defined in the section "Definitions of safety events".

Table 6. Safety Event Reporting Requirements

Safety event	Recorded on the CRF	Reported on the NIS AEM Report Form to Pfizer Safety within 24 hours of awareness
SAE ^a	All	All
Non-serious AE ^a	All	All
Scenarios involving exposure during breastfeeding, medication error, overdose, misuse, extravasation, lack of efficacy	All (regardless of whether associated with an AE/SAE)	All (regardless of whether associated with an AE/SAE) Note: Any associated AE/SAE is reported together with the exposure scenario.
Scenarios involving EDP	All (regardless of whether associated with an AE/SAE)	All (regardless of whether associated with an AE/SAE)
Scenarios involving occupational/environmental exposure	Not applicable	All (regardless of whether associated with an AE/SAE)

AE = adverse event; AEM = adverse event monitoring; EDP = exposure to a drug during pregnancy; NIS = non-interventional study; SAE = serious adverse event

For each safety event, the investigator must pursue and obtain information adequate both to determine the outcome of the AE and to assess whether it meets the criteria for classification as an SAE (refer to section "Serious Adverse Events" below).

Most often, the date of informed consent is the same as the date of enrollment. In some situations, there may be a lag between the dates of informed consent and enrollment. In these instances, if a patient provides informed consent but is never enrolled in the study (eg, patient changes his/her mind about participation, the reporting period ends on the date of the decision to not enroll the patient.

If the investigator becomes aware of an SAE occurring at any time after completion of the study and s/he considers the SAE to be related to lorlatinib, the SAE also must be reported to Pfizer DSU.

DEFINITIONS OF SAFETY EVENTS

Adverse events

An AE is any untoward medical occurrence in a patient administered a medicinal product. The event need not necessarily have a causal relationship with the product treatment or usage. Examples of AEs include but are not limited to:

- Abnormal test findings (see below for circumstances in which an abnormal test finding constitutes an AE)
- Clinically significant signs and symptoms
- Changes in physical examination findings
- Hypersensitivity
- Lack of efficacy
- Drug abuse

PFIZER CONFIDENTIAL

Drug dependency

Additionally, for medicinal products, they may include the signs or symptoms resulting from:

- Drug overdose
- Drug withdrawal
- Drug misuse
- Off-label use
- Drug interactions
- Extravasation
- Exposure during pregnancy
- Exposure during breastfeeding
- Medication error
- Occupational exposure

Abnormal test findings

The criteria for determining whether an abnormal objective test finding should be reported as an AE are as follows:

- Test result is associated with accompanying symptoms.
- Test result requires additional diagnostic testing or medical/surgical intervention.
- Test result leads to a change in study dosing or discontinuation from the study, significant additional concomitant drug treatment, or other therapy.
- Test result is considered to be an AE by the investigator or Sponsor.

Merely repeating an abnormal test, in the absence of any of the above conditions, does not constitute an AE. Any abnormal test result that is determined to be an error does not require reporting as an AE.

Serious adverse events

An SAE is any untoward medical occurrence in a patient administered a medicinal or nutritional product (including pediatric formulas) at any dose that:

- Results in death
- Is life-threatening
- Requires inpatient hospitalization or prolongation of hospitalization (see below for circumstances that do not constitute SAEs)
- Results in persistent or significant disability/incapacity (substantial disruption of the ability to conduct normal life functions)
- Results in congenital anomaly/birth defect

Since progression of underlying malignancy is being assessed as an efficacy variable, it should not be reported as an AE or SAE. The terms "Disease Progression", "Progression of Disease", or "Malignant disease progression" and other similar terms should not be used to describe an AE or SAE. However, clinical symptoms of progression may be reported as AEs or SAEs if the symptom cannot be determined as exclusively due to progression of the underlying malignancy or does not fit the expected pattern of progression for the disease under study. In addition, complications from progression of the underlying malignancy should be recorded as AEs or as SAEs in CRF.

Important Medical Event

Medical and scientific judgment is exercised in determining whether an event is an important medical event. An important medical event may not be immediately life-threatening and/or result in death or hospitalization. However, if it is determined that the event may jeopardize the patient or may require intervention to prevent one of the other outcomes listed in the definition above, the important medical event should be reported as serious.

Examples of such events are intensive treatment in an emergency room or at home for allergic bronchospasm; blood dyscrasias or convulsions that do not result in hospitalization; or development of drug dependency or drug abuse.

Suspected Transmission of an Infectious Agent

Additionally, any suspected transmission via lorlatinib of an infectious agent, pathogenic or non-pathogenic, is considered serious. The event may be suspected from clinical symptoms or laboratory findings indicating an infection in a patient exposed to lorlatinib. The terms "suspected transmission" and "transmission" are considered synonymous. These cases are considered unexpected and handled as serious expedited cases by pharmacovigilance (PV) personnel. Such cases are also considered for reporting as product defects, if appropriate.

Hospitalization

Hospitalization is defined as any initial admission (even if less than 24 hours) to a hospital or equivalent healthcare facility or any prolongation to an existing admission. Admission also includes transfer within the hospital to an acute/intensive care unit (eg, from the psychiatric wing to a medical floor, medical floor to a coronary care unit, neurological floor to a tuberculosis unit). An emergency room visit does not necessarily constitute a hospitalization; however, an event leading to an emergency room visit should be assessed for medical importance.

Hospitalization in the absence of a medical AE is not in itself an AE and is not reportable. For example, the following reports of hospitalization without a medical AE are not to be reported:

- Social admission (eg, patient has no place to sleep)
- Administrative admission (eg, for yearly exam)
- Optional admission not associated with a precipitating medical AE (eg, for elective cosmetic surgery)

PFIZER CONFIDENTIAL

- Hospitalization for observation without a medical AE
- Admission for treatment of a pre-existing condition not associated with the development of a new AE or with a worsening of the pre-existing condition (eg, for work-up of persistent pre treatment lab abnormality)

Causality assessment

The investigator is required to assess and record the causal relationship.

An investigator's causality assessment is the determination of whether there exists a reasonable possibility that lorlatinib caused or contributed to the safety event. For all safety events, sufficient information should be obtained by the investigator to determine the causality.

If the investigator's final determination of causality is "unknown" and s/he cannot determine whether lorlatinib caused the event, the safety event must be reported per the process outlined in Table 6.

If the investigator cannot determine the etiology of the event but s/he determines that lorlatinib did not cause the event, this should be clearly documented on the CRF and the NIS AEM Report Form.

Endpoint Adjudication Committee

Not applicable

Exposure During Pregnancy, Exposure During Breastfeeding, Environmental Exposure and Occupational Exposure

Exposure during pregnancy

Prospective and retrospective exposure during pregnancy (EDP) reports are reportable using the NIS AEM Report Form and the EDP Supplemental Form, irrespective of the presence of an associated safety event.

The procedures for reporting as per Table 6 should be followed.

If the mother or the fetus experience a safety event during administration of such drugs, the safety event must be reported without the event EDP reported.

An EDP occurs if:

- A female participant becomes, or is found to be, pregnant either while receiving or having been exposed to lorlatinib, or the female becomes, or is found to be, pregnant after discontinuing and/or being exposed to lorlatinib (maternal exposure).
- A male participant who is receiving or has discontinued lorlatinib inseminates a female partner prior to or around the time of conception and/or during the partner pregnancy.
 - In this case, the study participant will be provided with the Pregnant Partner Release of Information Form to deliver to their partner. It must be documented that the study participant was given this letter to provide to their partner.

All reports submitted should include the anticipated date of delivery, as applicable, and should be managed as follows:

- Follow-up is conducted to obtain general information on the pregnancy; in addition, followup is conducted to obtain information on EDP outcome for all EDP reports with pregnancy outcome unknown.
- A pregnancy is followed until completion or until pregnancy termination (eg, induced abortion) and Pfizer is notified of the outcome. This information is provided as a followup to the initial EDP report.
- In the case of a live birth, the structural integrity of the neonate can be assessed at the time of birth.
- In the event of a termination, the reason(s) for termination should be specified and, if clinically possible, the structural integrity of the terminated fetus should be assessed by gross visual inspection (unless pre-procedure test findings are conclusive for a congenital anomaly and the findings are reported).
- If the outcome of the pregnancy meets the criteria for an SAE (eg, ectopic pregnancy, spontaneous abortion, intrauterine fetal demise, neonatal death, or congenital anomaly [in a live born, a terminated fetus, an intrauterine fetal demise, or a neonatal death]), the procedures for reporting SAEs should be followed.

Additional information about pregnancy outcomes that are reported as SAEs:

- Spontaneous abortion includes miscarriage and missed abortion
- Neonatal deaths that occur within 1 month of birth should be reported, without regard to
 causality, as SAEs. In addition, infant deaths after 1 month should be reported as SAEs
 when the HCP assesses the infant death as related or possibly related to exposure to
 investigational product.

Additional information regarding the EDP may be requested. Further follow-up of birth outcomes will be handled on a case-by-case basis (eg, follow-up on preterm infants to identify developmental delays).

Exposure during breastfeeding

Exposure during breastfeeding (EDB) is reportable using the NIS AEM Report form, irrespective of whether a safety event has occurred. The procedures for reporting as per Table 6 should be followed.

An EDB occurs if:

· A female participant is found to be breastfeeding while receiving or after discontinuing lorlatinib.

Environmental/Occupational Exposure:

Environmental or occupational exposure occurs when a person not enrolled in the study as a participant receives unplanned direct contact with or exposure to lorlatinib. Such exposure may or may not lead to the occurrence of a safety event. Persons at risk for environmental or occupational exposures include healthcare providers, or family members, who may be exposed. Any such exposures to lorlatinib are reportable to Pfizer DSU within the timelines outlined in Table 6 and irrespective of the presence of an associated safety event. Since the information about the occupational exposure does not pertain to a participant enrolled in the study, the information is not recorded on CRF; however, a copy of the completed NIS SAE Report Form must be maintained in the investigator site file.

Below are examples of environmental/occupational exposure:

- A nonparticipant (a family member or an HCP that has been accidentally exposed to lorlatinib by all possible routes of exposure, eg, ingestion, inhalation, or skin contact and then developed an AE/SAE.
- A male nonparticipant (eg, male family member or a male HCP) who has been exposed to lorlatinib by all possible routes of exposure, eg, ingestion, inhalation, or skin contact then inseminates his female partner prior to or around the time of conception.
- A female nonparticipant (eg, female family member or female HCP) is found to be pregnant or breastfeeding while being exposed or having been exposed to lorlatinib (ie, environmental exposure) by all possible routes of exposure, eg, ingestion, inhalation, or skin contact.

Medication error

A medication error is any unintentional error in the prescribing, dispensing, or administration of a medicinal product that may cause or lead to inappropriate medication use or patient harm while in the control of the health care professional, patient, or consumer.

Such events may be related to professional practice, health care products, procedures, and systems including prescribing; order communication; product labeling, packaging, and nomenclature; compounding; dispensing; distribution; administration; education; monitoring; and use.

Medication errors include:

- Near misses, involving or not involving a patient directly (eg, inadvertent/erroneous administration, which is the accidental use of a product outside of labeling or prescription on the part of the healthcare provider or the patient/consumer)
- Confusion with regard to invented name (eg, trade name, brand name).

The investigator must submit the following medication errors to Pfizer DSU within the timelines outlined in Table 6, irrespective of the presence of an associated safety event:

- Medication errors involving patient exposure to the product, whether or not the medication error is accompanied by a safety event.
- Medication errors that do not involve a patient directly (eg, potential medication errors or near misses).

When a medication error does not involve patient exposure to the product the following minimum criteria constitute a medication error report:

- An identifiable reporter
- A suspect product
- The event medication error

Overdose, Misuse, Extravasation

Reports of overdose and misuse associated with the use of lorlatinib are reported to Pfizer DSU by the investigator, irrespective of the presence of an associated safety event as per Table 6.

Lack of Efficacy

Reports of lack of efficacy of lorlatinib are reported to Pfizer DSU by the investigator, irrespective of the presence of an associated safety event or the indication for use of lorlatinib as per Table 6.

